Form CT

UTHSA Clinical Trial Description

This form is not mandatory. Other documents are acceptable if equivalent information is provided.

UTHSCSA Tracking Number (internal use only)	20220493H	1. Original Version Date	6/4/2022
		1.1. Revision Date(s) add rows as needed	8/11/2022

Title: Mechanisms to Reduce Mental and Physical Fatigue Following Exercise Training in Older Adults

2. Background

Briefly discuss the important literature relevant to the trial and that provides background for the trial. Include the importance of the trial and any relevant treatment issues or controversies.

Background and Significance

Aging Associated Fatigue: The prevalence of self-reported mental and physical fatigue among older adults is at least 25% in primary care settings (Hickie et al., 1996). Mental fatigue refers to a decrease in cognitive resources, while physical fatigue refers to the inability of muscles to maintain optimal performance. Studies suggest that mental fatigue may be present before the onset of disability and morbidity (Avlund et al., 2003) and has been reported by older adults to be a main reason for activity restriction and poor compliance with exercise interventions (Cooper et al., 2001). Though prior studies show that both components are associated with low-grade inflammation, more research is needed to pinpoint specific biological pathways to connect chronic inflammation to fatigue-associated health declines.

Mechanisms Leading to Fatigue in Older Adults: One pathway that may play an integral role in fatigue progression is that of the essential amino acid, tryptophan. Normally, 90-95% of tryptophan is metabolized along the kynurenine pathway in the liver. Inflammation upregulates kynurenine pathway enzymes outside the liver, causing intracellular and circulating kynurenine or oxidative kynurenine metabolite concentrations to rise. The accumulation of kynurenine and its oxidative metabolites are strongly associated with physical fatigue including weaker grip strength and slower walking speed (Westbrook et al., 2020). Further, they can readily cross into the central nervous system (**CNS**) and underlie the behavioral and cognitive impairments caused by inflammation (Allison et al., 2014).

[figure not shown]
Tryptophan Metabolism as a Mechanism Influencing Fatigue During Exercise: Evidence in animal models suggests that reductions in physical fatigue often observed with exercise training are mediated by skeletal muscle peroxisome proliferator-activated receptor γ co-activator 1 α (**PGC-1 α**), inducing a shift of kynurenine to kynurenic acid ((Agudelo et al., 2014; Agudelo et al., 2019). This is catalyzed by kynurenine aminotransferase (**KAT**) enzymes, which prevents oxidative metabolism of kynurenine and also its entry into the CNS, which may have an influence on mental fatigue. We have shown that reductions in skeletal muscle inflammation are associated with reductions in mental and physical fatigue following exercise training (Serra et al., 2018); however, a recent study in older adults also found that exercise training significantly increased skeletal muscle PGC-1 α gene expression and KAT isoforms nearly two-fold (Allison et al., 2019). These data suggest that the tryptophan metabolism pathway may play an integral role in regulating mental and physical fatigue with exercise.

Though we have shown that exercise training can reduce the incidence of moderate-to-severe mental and physical fatigue by 30-60%, we also find that 82% of subjects continued to report mild fatigue after the intervention (Serra et al., 2018).

Further, our preliminary data suggest that when participating in exercise training, older adults tend to reduce their free-living activity by ~20% and report acute fatigue follow exercise as a contributing factor. Therefore, identifying methods to prevent acute fatigue during exercise and maximize the fatigue-reducing abilities of chronic exercise training in older adults is needed.

Potential of Branched-Chain Amino Acid Supplementation to Reduce Mental and Physical Fatigue When Combined Exercise: Exhaustive exercise results in the branched-chain amino acids (**BCAA**: leucine, isoleucine and valine) being taken up by the muscle, leading to reductions in the plasma concentration. When consumed as a nutritional supplement, BCAAs may improve circulating concentration of physical fatigue substances (lactate, ammonia and 5-hydroxytryptamine), energy metabolites (glucose and free fatty acids) and muscle soreness substances (lactate dehydrogenase

Figure 1. Conceptual Model: The addition of BCAA to exercise activates PGC-1 α to convert kynurenine to kynurenic acid (a metabolite unable to cross the blood-brain barrier), thereby preventing mental and physical fatigue. Adapted from Agudelo et al. (6).

and creatine kinase) (Kim et al., 2013), leading to improved physical performance. In the past two decades, numerous studies have shown the advantageous effects of BCAAs on acute and chronic exercise performance, including improvements in time to exhaustion and strength (Kephart et al., 2016; AbuMoh'd et al., 2020).

Further, studies in animal models suggest that BCAAs decreases the transport of tryptophan and its metabolites into the CNS because BCAAs and tryptophan compete for the same carrier system. We have recently shown that depletion of plasma BCAAs following dialysis is highly associated with mental fatigue (Debnath et al., 2020). In animal models, BCAAs attenuate changes in skeletal muscle PGC-1 α mRNA caused by acute exercise by ~50% (Samuelsson et al., 2016). Though currently unexplored, these data suggest that when combined with exercise, BCAA supplementation may have the ability to modify mental and physical fatigue by modulating the tryptophan pathway (Figure 1).

3. Objectives and Endpoints *All data points collected in the study should support an objective or have a regulatory purpose. Complete the table – add rows as needed.*

3.1. Objective(s) Clearly and concisely define the primary and secondary outcomes.	3.2. Endpoint Clearly define the endpoints. (endpoints are the basis for concluding that the objective has been met).	3.3. Justification for Endpoint Briefly explain why the endpoint(s) were chosen.
This study will address two significant objectives that are critical to aging adults. First, we will examine whether the addition of BCAA to acute and chronic exercise has the ability to reduce mental and physical fatigue. The identification of BCAA added to exercise as superior to exercise alone could have clinical implications for older adults to improve cardiometabolic and functional risk. By reducing fatigue, older adults may be able to engage in longer periods of physical activity, thereby reducing weight gain common to older adults and improving mental and physical quality of life. This study also will address an innovative mechanistic question. This study will begin to fill a knowledge gap by determining whether changes in tryptophan metabolism occur following exercise with and without BCAA supplementation and relate to reductions in mental and physical fatigue as this may identify potential targets for future (lifestyle and pharmacologic) investigation.	Depending on which group a subject is randomized to: 1) Completion of 8 weeks of EX+BCAA 2) Completion of 8 weeks of EX+PLA (placebo) We hypothesize that 8 weeks of EX+BCAA will 1) reduce mental and physical fatigue and 2) increase PGC-1 α , KATs, and kynurenic acid and decrease oxidative kynurenines compared to EX+PLA.	Justification for endpoint comes from the data generated in the past two decades that have shown the advantageous effects of branched-chain amino acids (BCAAs) on exercise performance. Further, studies in animal models suggest that BCAAs decrease the transport of tryptophan and its metabolites into the CNS because BCAAs and tryptophan compete for the same carrier system. Thus, combining BCAA with exercise may synergize to divert metabolism away from formation of neurotoxic tryptophan metabolites with known deleterious effects on mental and physical fatigue.

4. Rationale

Briefly state the reason for conducting the clinical trial.

The rationale of this study comes from the data generated in the past two decades that have shown the advantageous effects of branched-chain amino acids (BCAAs) on exercise performance. Further, studies in animal models suggest that BCAAs decrease the transport of tryptophan and its metabolites into the CNS because BCAAs and tryptophan compete for the same carrier system.

5. Study Design: Double blind Randomized Controlled Trial

5.1. Number of Groups/Arms		2 arms, 15 participants per arm 30 screened and enrolled (n=24 completers)	Group name(s)	exercise plus placebo (EX+PLA) vs. exercise plus BCAA (EX+BCAA)								
5.2. Overall Design Select all applicable												
	Randomization				Cluster Randomized							
	Group-Sequential				Adaptive Design							
	Parallel Design				Placebo-Controlled							
	Superiority				Equivalence				Non-inferiority			
Device		Pilot			Pivotal				Post-Approval			
Drug/Biologic		Phase 1		Phase 1/2		Phase 2		Phase 2/3		Phase 3		Phase 4
	Dose escalation		If yes, details →									
	Dose ranging		If yes, details →									
	Sub-studies		If yes, details →									
5.3. Other Design Details: Experimental Test by Phase: The experimental design of this study involves 5 phases, completed over 3-4 months. Phase 1 involves recruitment, screening, and enrollment. Phase 2 involves baseline testing. Volunteers then will be randomly assigned to exercise plus placebo (EX+PLA) vs. exercise plus BCAA (EX+BCAA) (Phase 3). Randomization will be 1:1 using a random number generator, assigning participants down the list in order of eligibility. Phase 4 consists of eight weeks of either 3x/week EX+PLA or EX+BCAA. After the intervention, subjects will undergo final research testing (Phase 5). All research testing and training will occur at the Barshop Institute. Intervention staff and participants will be blinded (double blinded) to supplement allocation. Participants will receive either a supplement or a placebo, both in powder form. Only study team member without direct participant interaction (i.e., statistician) will know supplement allocation. Refer to section 10.1 for further information on randomization and blinding.												

6. Study Population									
6.1. Study Population(s) Label/Name To add more populations – select a row, copy & paste			6.2. Identify the criteria for inclusion The criteria that every potential participant must satisfy, to qualify for study entry.				6.3. Identify the criteria for exclusion The characteristics that make an individual ineligible for study participation.		
			All individuals in this study population must meet all of the inclusion criteria in order to be eligible to participate in the study				All individuals in this study population meeting any of the exclusion criteria at baseline will be excluded from study participation.		
30 screen and enrolled (n=24 completers); 15/group; Community-dwelling older adults, age 60-80 years of age, with subjective reporting of fatigue (reporting ≥3 on a 1-10 fatigue scale)			
 1) fatigue (participants reporting ≥3 on a 1-10 scale) 2) 60-80 years of age 3) lack of menses for at least one year for women 4) BMI 20-50 kg/m² 5) untrained with regard to structured exercise training (is not currently training more than 2x/week) 				
 1) taking an anticoagulant medication that is unable to be discontinued before biopsies 2) allergic to lidocaine 3) neurologic, musculoskeletal, or other condition that limits subject's ability to complete study physical assessments or training 4) hepatic (LFTs >2.5xWNL), renal (eGFR<45), , and uncontrolled psychiatric disease 5) cognitive impairment (MoCA<21) 		

		6) consuming uncommon supplements (multivitamin, calcium, vitamin D, etc are okay)
		7) uncontrolled depression (CESD \geq 16)
		8) any disease or condition considered to be exclusionary based on the clinical opinion and discretion of the PI
6.4. Will screen failures be allowed to re-screen at a later date?	 No  Yes	If yes, describe criteria below ↓ If participants are able to address criteria for exclusion (e.g., stop taking uncommon dietary supplements), they can be considered for rescreening at a later date.

7. Study Intervention(s) being tested or evaluated

This can include prevention, diagnostic or therapeutic interventions (e.g., drug or device) or educational, health services or basic science interventions (e.g., educational program, health care delivery model, or examining basic physiology)

Experimental Test by Phase: The experimental design of this study involves 5 phases, completed over approximately 3-4 months. *Phase 1* involves recruitment, screening, and enrollment. *Phase 2* involves baseline testing. Participants then will be randomly assigned to exercise plus placebo (**EX+PLA**) vs. exercise plus BCAA (**EX+BCAA**) (*Phase 3*). *Phase 4* consists of eight weeks of either 3x/week EX+PLA or EX+BCAA. After the intervention, participants will undergo final research testing (*Phase 5*). All research testing and training will occur at the Barshop Institute.

Participant Recruitment, Screening, and Enrollment (Phase 1):

Recruitment: We will recruit participants from the Clinics of UT Health San Antonio and the Clinical Research Core of the San Antonio Older Americans Independence Center. Additionally, recruitment methods may include posting study fliers in medical offices or senior centers, community engagement activities, and/or newspaper or web-based advertisements including social media. A UT Health website to present the project to the public will be published online and could be referenced by other institutional websites. We will recruit men and women of all races and ethnic backgrounds. The study will be published on clinicaltrials.gov. Telephone pre-screening prior to the clinic screening visit may be employed to ensure potential candidates will meet inclusion and exclusion criteria for enrollment. Those who qualify preliminarily will be scheduled for a full in-clinic evaluation and will be provided an advance copy of the consent form. All these strategies will be considered, made available and implemented/adapted according to the local policies and regulations.

Screening: Eligible volunteers will have the study explained and provide informed consent according to the guidelines of the UT Health San Antonio IRB. Participants will be asked to supply the name and contact information of their primary care provider during the consent/screening phase. An in-clinic evaluation consisting of medical history and physical exam (including EKG) will be conducted by a research clinician. Information on demographics and family medical history will be recorded. A fasting blood profile for lipids, liver, renal and hematological function will be drawn. We will draw approximately 30 ml of blood (about 2 tablespoons) during screening (*Phase 1*). Although we do not expect a problem with the collection of blood samples, should a problem arise, such as clotting or insufficient sample for analysis, we may draw additional blood, not exceeding 50 ml (10 teaspoons) throughout any study visit. Height and weight will be measured using a standard physician's scale. Seated blood pressures will be measured. Questionnaires to screen for depression and cognitive impairment will be administered to determine eligibility.

Enrollment: Participants will be enrolled if they provide informed consent and pass all required screening assessments.

Baseline Research Testing (Phase 2): Data for primary and secondary outcomes will be collected using standardized protocols and trained staff. All baseline testing will be conducted at the Barshop Institute over approximately 3-4 visits during approximately 2-4 week period. These tests are described in detail below.

Randomization (Phase 3): Assigned (1:1 randomization) to either EX+PLA or EX+BCAA. After randomization, vital signs and blood will be drawn before (following a 12 hour fast) and acutely (3-5 min) after completing a 400 m walk test. After the fasting blood draw, participants will receive (blinded) either ~7-10 g of BCAAs (100 mg/kg) or maltodextrin (depending upon group allocation) 30 min prior to beginning this test. Heart rate and ratings of perceived exertion will be collected throughout the 400 m walk test. Participants will be instructed to document their food intake on Food Record form during the 2 days before the 400 m walk test and to repeat this diet before the post intervention test.

Exercise + Placebo or Exercise + BCAA (Phase 4):

Exercise: The 3x/wk for eight weeks exercise protocol is designed to provide a high-volume, moderate-intensity whole body training stimulus for all participants. The sessions will occur at the Barshop Institute and be led by an exercise physiologist.

Aerobic exercise training will start conservatively with a goal of 30 minutes total duration at 40-50% maximal heart rate reserve (HRR) determined according to the formula of Karvonen: Training HR = % (HRmax - HRrest) + HRrest. HRmax is defined as peak heart rate based during a peak Cardiopulmonary Exercise Test (described above). Treadmill exercise is advanced weekly, as tolerated to an intensity of 75-85% HRR for 30 minutes. Additionally, participants will perform resistance exercise consisting of 15 repetitions for two sets and to exhaustion on the third set for five major muscle groups: chest press, knee extension, leg curl, row, and bicep curl. Resistance is gradually increased to account for strength gains when participants are able to complete 20 repetitions on the third set.

BCAA or Placebo: Participants will be randomized 1:1 to eight weeks of BCAA or maltodextrin (PLA) supplementation. Participants will be instructed to consume either ~7-10 g of BCAAs (100 mg/kg body weight) (2:1:1 leucine:isoleucine:valine) or PLA powder. In the Barshop Institute pharmacy, intervention blinded study staff wearing hair net, gloves and a facemask will weigh the required participant dose via nutrition food scale and place the daily dose in disposable condiment containers and labeled with dates for daily intake. Powders will be distributed in a double-blind fashion, identical in color, and dissolved in water or a non-calorie drink of their choice (i.e., Crystal Light). On non-exercise days, participants will be instructed to take the supplement between 9 - 10 am each morning and to log each intake in a provided spreadsheet. Powders to be consumed on non-exercise days will be pre-packaged containers and provided to participants on a weekly basis. On exercise days, the supplement will be consumed immediately after finishing exercise training. Supplement containers also will be returned every two weeks to track compliance. Assessment of side effects will occur at every exercise session.

Post Intervention Testing (Phase 5): Participants will repeat tests outlined in Phase 2 and the submaximal exercise test outlined in Phase 3.

Early Withdrawal of Subjects: If subjects are withdrawn prematurely from the study, appropriately designated research staff will make efforts to collect data throughout the protocol defined follow-up period for that subject. If a subject withdraws consent to participate in the study, attempts will be made to obtain permission to record data up to the protocol-described end of subject follow-up period. Investigator and designated research staff make it a high priority to obtain data on all subjects lost to follow up. Lost to follow up will be defined as a subject missing 3 or more consecutive visits without reasonable explanation, not answering or responding to 3 follow up phone calls to subject or emergency contacts, or returned receipt of 1 certified letter.

8. Protocol-Directed procedures, items, services or tests

List all procedures directed by the study plan - including items or services provided as part of routine or conventional care and those needed to diagnosis or treat research related complications.

Important Note – The protocol directed procedures listed must match those in the Schedule of Activities (attachment)

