8.6. Other Research Procedures (e.g., other safety and efficacy assessments.)

Study Procedures:

- a) Questionnaires related to their health-related quality of life (PROMIS-57), fatigue assessment scale (FAS), Center for Epidemiologic Studies Depression Scale (CES-D), energy expenditure (Minnesota Leisure Time Physical Activity Questionnaire; MLTQ), activities of daily living, and dietary habits (short health eating index: sHEI) and sleep quality (Insomnia Severity Index: ISI). See Form M.
- b) Body composition: Minimum and maximum waist and hip circumference will be measured with a tape measure. Weight will be measured on a standard physician's scale.
- c) Energy Intake and Expenditure: *Energy intake* will be assessed through the Automated Self-Administered 24-Hour (ASA24®) Dietary Assessment Tool. Participants will be asked to self-administer 24-hour food recalls over a 3-5-day period and enter the information into the ASA24® web-based tool that enables multiple, automatically coded, self-administered 24-hour recalls. The latest release, ASA24-2016, also permits researchers to collect data using multi-day food records, also known as food diaries. Simultaneously, an activity monitor (Actigraph™) system will be used to monitor *total daily activity energy expenditure* (kcal/d). The Actigraph™ GT9x-BT accelerometers will be provided to participants upon meeting eligibility criteria. The monitors will be worn either on a belt around the hip or the wrist as he or she would a watch. Participants will wear the accelerometer for 5-7 days including the weekend. This measurement will be taken prior to randomization (Phase 3).
- d) Physical Fatigue:

Isometric Handgrip: Hand grip strength of both limbs will be assessed using a handheld dynamometer.

Strength: We will use a standardized 1-repetition maximum (1-RM) protocol that includes 4-6 trials with rest periods of the leg extension and chest press exercises. Participants also will be asked to perform the leg extension and chest press exercises at 60% 1-RM as many times as they can before fatigue.

Chair rise: The number of times that a participant can rise from a sitting to a standing position and to sit down again as quickly as they can in 30 seconds will be recorded. The time for the participants to rise five times from a sitting to a standing position and to sit down again also will be recorded.

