	N/A - An Investigator Brochure is attached
	N/A - A Drug/Device Manual is attached
9.1. Acquisition and accountability State how the study intervention and control product will be provided to the investigator. Describe plans about how and by whom the study intervention will be distributed, including participation of a drug repository or pharmacy, and plans for disposal of expired or return of unused product.	

This study will utilize over-the-counter dietary supplement powders, neither of which require regulation by the FDA. Each will be purchased online and shipped to the Barshop Institute and stored in the clinical pharmacy.
 
The BCAA supplement we will utilize is manufactured and distributed by Naked Nutrition. 1 scoop (1Tbsp) contains 2500 mg of L-leucine, 1250 mg of L-isoleucine, and 1250 mg of L-valine and sunflower lecithin.
 
The maltodextrin placebo we will utilize is manufactured and distributed by nutricost. 1 scoop (15 g) contains 14 g of carbohydrate (maltodextrin).
 
Study staff will distribute the supplement to participants weekly and will ask for unused containers to be returned weekly. The distribution of supplement will be logged by study staff. Participants also will keep a log of supplement intake.
 
Expired and returned product will be discarded following pharmacy protocol.
	
9.2. Formulation, Appearance, Packaging, and Labeling Describe the formulation, appearance, packaging, and labeling of the study intervention and control product, as supplied. Information in this section can usually be obtained from the IB or the package insert, or device labeling. This section should include the name of the manufacturer of the study intervention and control product.	

Intervention blinded study staff wearing hair net, gloves and a facemask will weigh the required participant dose via nutrition food scale and place the daily dose in disposable polypropylene condiment containers and labeled with dates for daily intake.
	
9.3. Product Storage and Stability Describe storage and stability requirements (e.g., protection from light, temperature, humidity) for the study intervention and control product. For studies in which multi-dose vials are utilized, provide additional information regarding stability and expiration time after initial use (e.g., the seal is broken).	

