
The supplement will be stored per distributor recommendations (cool, dry place) in the Barshop clinical pharmacy.
	
9.4. Preparation Describe the preparation of the study intervention and control product, including any preparation required by study staff and/or study participants. Include thawing, diluting, mixing, and reconstitution/preparation instructions in this section. For devices, include any relevant assembly or use instructions.	

On exercise days, both powders will be dissolved in ~400 ml of a non-caloric drink of their choice (i.e., Crystal Light) in the clinical pharmacy by study staff. On non-exercise days, participants will be provided with the Crystal Light and provided written instruction to prepare the mixture.
	

10. Study Intervention Additional Details	
10.1. Measures to Minimize Bias: Randomization and Blinding This section should contain a description of randomization and blinding procedures (if applicable to the study design). It should include a description or a table that describes how study participants will be assigned to study groups, without being so specific that blinding or randomization might be compromised. Plans for the maintenance of trial randomization codes and appropriate blinding for the study should be discussed. The timing and procedures for planned and unplanned breaking of randomization codes should be included. Include a statement regarding when unblinding may occur and who may unblind. Provide the criteria for breaking the study blind or participant code. Discuss the circumstances in which the blind would be broken for an individual or for all participants (e.g., for serious adverse events (SAEs)). Indicate to whom the intentional and unintentional breaking of the blind should be reported.	

Randomization codes will be created at random and kept electronically by a study team member not directly involved with participants (i.e., statistician). We anticipate that blinding will only be broken prior to completion of the study if requested by the DSMB due to safety concerns. Unblinding prior to study completion will be reported to the IRB, study sponsor and DSMB.
 
Randomization code: a random number generator will be used utilizing numbers 1 and 2 where 1=placebo group 2= BCCA group
	

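### The powders are stated to match only in form and colour, Sections 7 and 9.4 differ on the drink, and no check of the blind is described, so self-reported fatigue is open to expectation bias if participants recognise their product

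*Combined protocol and SAP*

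**What the plan says.** **Matching.** Section 5.3 states: "Participants will receive either a supplement or a placebo, both in powder form". Section 7 (Phase 4, BCAA or Placebo) adds colour and the drink: "Powders will be distributed in a double-blind fashion, identical in color, and dissolved in water or a non-calorie drink of their choice", with Crystal Light then named in parentheses. Taste, smell, texture, solubility and volume of powder are not addressed, and no placebo amount per dose is given.

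**Products.** Section 9.1 describes the BCAA powder: "1 scoop (1Tbsp) contains 2500 mg of L-leucine, 1250 mg of L-isoleucine, and 1250 mg of L-valine and sunflower lecithin". The placebo is a maltodextrin powder from a different manufacturer.

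**Drink and mixing.** For exercise days, Section 9.4 says "both powders will be dissolved in ~400 ml of a non-caloric drink of their choice (i.e., Crystal Light) in the clinical pharmacy by study staff". For other days it says "On non-exercise days, participants will be provided with the Crystal Light and provided written instruction to prepare the mixture". Water is not mentioned there. The Phase 3 text on the 400 m walk test calls the dose blinded but names no drink.

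**Protection and monitoring of the blind.** Sections 5.3 and 10.1 cover who holds the codes and unblinding requested by the DSMB. Section 10.2 covers intake logs and returned product. None of these asks whether participants or trainers have guessed the allocation.

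**Outcomes.** Section 12.4 names fatigue and tryptophan metabolism as the primary outcomes. Section 8.6 lists FAS and PROMIS-57 among the questionnaires and performance tests under physical fatigue. Phase 3 adds ratings of perceived exertion during the walk.

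**The concern.** The two arms differ only in the powder, so the participant blind is the main protection for any outcome that a participant reports. The text commits the sponsor to two similarities between chemically different products. It then leaves the drink partly to the participant, and one section allows plain water, which would mask little. Someone who takes an unflavoured dose, or who handles the dry powder several times a week, may form a view of what it is.

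If beliefs about allocation differ between arms, participants who think they are on BCAA may report less fatigue, which is the direction of the hypothesis. Without a record of those beliefs, a favourable fatigue result could not be examined for this explanation. Section 12.2 also says that a goal is to obtain effect sizes for later studies, so a bias too small to reach significance could still be carried into their planning.

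**Working it through.** **1. The two sections on the drink, side by side**

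| | Section 7, Phase 4 | Section 9.4 |
|---|---|---|
| Plain water | Permitted | Not mentioned |
| Exercise days | Water or non-calorie drink, participant's choice | Non-caloric drink, participant's choice, about 400 ml, mixed by staff |
| Non-exercise days | Same wording as for exercise days | Crystal Light supplied, mixed by participant; no volume given |

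The sections agree that a flavoured drink may be used. They disagree on whether water is allowed, and neither fixes one product and flavour for everyone.

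**2. Share of doses mixed by the participant**

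Inputs, both from Section 7: daily dosing ("place the daily dose in disposable condiment containers and labeled with dates for daily intake") and three sessions a week ("The 3x/wk for eight weeks exercise protocol").

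- Supplement days: 8 × 7 = 56.
- Exercise days: 8 × 3 = 24.
- Days mixed at home: 56 − 24 = 32, and 32/56 = 57%.

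This counts days on which the participant handles dry powder. It does not count days without a flavoured drink.

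**3. What an expectation shift would do to the planned test**

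The plan gives no figure here to reproduce. Inputs: 12 completers per arm (Section 12.2), a two-sided independent-samples t-test (Section 12.4) at the 5% level (Section 12.2), and no true effect. The shift *d*, in SD units of the self-reported outcome, is an assumption.

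- Degrees of freedom: 12 + 12 − 2 = 22; critical value 2.074.
- Noncentrality: *d* × √(12/2) = *d* × √6.
- False-positive rate: P(|T| > 2.074), with T noncentral t.

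| Assumed shift between arms | Noncentrality | False-positive rate |
|---|---|---|
| 0.1 SD | 0.245 | 5.6% |
| 0.25 SD | 0.612 | 9.0% |
| 0.5 SD | 1.225 | 21.6% |

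**4. From belief to a shift between arms**

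A belief effect separates the arms only as far as beliefs differ between them. If a fraction *p* in each arm guesses correctly, the share believing they take BCAA is *p* in one arm and 1 − *p* in the other. The shift is then (2*p* − 1) × belief effect. With *p* = 0.70, also assumed:

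- belief effect 0.5 SD: 0.4 × 0.5 = 0.2 SD, false-positive rate 7.6%;
- belief effect 0.25 SD: 0.4 × 0.25 = 0.1 SD, false-positive rate 5.6%.

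**5. What a guess question can show in 24 completers**

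Under an exact two-sided 5% binomial test against 50%, at least 18 of 24 correct guesses are needed (17 gives p = 0.064, 18 gives p = 0.023). The chance of reaching 18 is 39% if the true rate of correct guessing is 70%, and 81% if it is 80%. Guess data at this size can describe the blind but cannot certify it.

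**The case against.** The strongest reply is that the design already masks the products. Section 9.4, the detailed preparation section, has a flavoured drink in use at the centre and at home, and plain water appears once, as an alternative, in Section 7. Doses are weighed by staff into the same kind of dated container. No participant receives both products, so nobody can compare them directly. Section 6.3 excludes people taking uncommon supplements, which makes current familiarity with BCAA powder less likely. Tryptophan metabolism is also a primary outcome, and the sample size rests on kynurenine concentration, which is not self-reported.

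Most of this stands, and it limits the point in four ways.

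- A reader might infer that participants can identify their product. The documents give no taste, smell, texture or solubility data, and the short product descriptions in Section 9.1 do not show that flavouring is absent. They support only that recognition is possible.
- A reader might infer that the powders are taken unmasked on most days. The 57% is home mixing, for which Section 9.4 supplies a flavoured drink.
- A reader might infer that nothing planned would reveal a failed blind. The Schedule of Activities and Form M are attachments not among the documents reviewed, so one can say only that the text describes no check.
- A reader might take 21.6% as the expected error rate. It needs a 0.5 SD shift between arms, which means near-complete recognition or a belief effect larger than 0.5 SD.

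The reply leaves three things unanswered: Section 7 does allow water, the drink is still a matter of choice in both sections for exercise days, and participants handle dry powder that is described as matching only in form and colour.

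**Conclusion.** The concern holds in a limited form. Stated matching stops at form and colour, Sections 7 and 9.4 must be reconciled on the drink, 32 of 56 doses are self-mixed, and no check of the blind is described. Participants may be able to recognise their product; that they will is not shown.

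The exposure is greatest for FAS, PROMIS-57 and perceived exertion. It is smaller for effort-dependent tests such as 1-RM and repetitions to fatigue, and the tryptophan metabolites are largely unaffected.

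The false-positive rates of 5.6% to 21.6% illustrate what a shift of 0.1 to 0.5 SD would do. They assume 12 completers per arm, no true effect and a shift for which the documents give no source. The change is worth making because it is specific and cheap, and because guesses not collected during the trial cannot be reliably recovered afterwards.

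**What to change.** **Drink.** Reconcile Section 7 (Phase 4) and Section 9.4. Delete the plain-water option and the free choice, and specify one flavoured non-caloric drink mix, with the same product, flavour and volume, for all participants on all days. Apply it to the doses given before the 400 m walk tests as well. Serve it in opaque lidded cups at the centre and supply the same cups for home use.

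**Matching.** State in Section 9.2 what is matched beyond form and colour. The common drink and cup do not hide dry powder opened at home, so the text should not claim more than is done.

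**Check of the blind.** Add one question at Phase 5 in which participant and trainer each guess the allocation. Ask it only after all fatigue questionnaires and effort tests are complete, so that it cannot influence the answers. Report guesses descriptively by arm. With about 24 completers, do not use them as a formal test or as an adjustment.

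**Cost.** Protocol wording, one bulk purchase of drink mix, cups and one question at an existing visit. The downside is that participants lose their choice of drink, which may slightly affect palatability.
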